6.1.4. Administration of AV7909

AV7909 will be administered to all participants in all groups as a 0.5 mL IM vaccination in alternate arms on Days 8 and 23. Vaccinations will be administered in the clinic by authorized personnel once AEs have been assessed, vitals have been taken and a symptom-directed PE conducted. Females who have not demonstrated an FSH level >30 mIU/mL must also pass a urine pregnancy test (see [Section 8.3.2](#)).

Participants in Groups 1A and 2A will receive their first vaccination after the 12-hour PK sample in the evening of Day 8, and their second vaccination on Day 23. Site personnel who administer the vaccine should be trained in the early recognition of symptoms of anaphylactic reactions, a rare but potentially serious reaction to parenteral injections.

Sites should be prepared to treat participants experiencing clinically significant dyspnea or hypotension, wheezing or generalized urticarial reactions. Appropriate medical therapy for anaphylaxis should be administered, if indicated, which should include IM or subcutaneous epinephrine 1:1000, and may include corticosteroids, diphenhydramine, bronchodilators, intravenous volume expansion, and/or oxygen. Participants will be evaluated and carefully monitored until complete resolution of any signs and symptoms, should they occur.

If a participant in Groups 1 or 2 has a moderate or severe illness and/or an oral temperature greater than 100.4°F within three days before vaccination 1, or any condition that, in the opinion of the Investigator, would render vaccination unsafe or would interfere with evaluations, these participants will be withdrawn from the study and will be considered ineligible for rescreening. These participants will be instructed to cease taking antibiotics but to continue with their e-diary for an additional 7 days beyond the day they ceased taking antibiotics at which point they will be asked to return to the site and complete the EWV procedures. If the reason for not receiving vaccine is an AE/SAE/AESI, the participants will be followed until the event has resolved, stabilized or the participant has been referred to another physician. These participants, having not received any vaccine, will not be included in the long-term follow-up nor will they have additional blood samples taken for TNA, TSH or autoantibodies.

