6.5.1.1. Medications Prohibited Due to Effects on Inflammation or the Immune System

Prohibited and restricted medications for all participants include anti-inflammatory or antipyretic medications, topical antihistamine eye drops, nasal steroids, vaccines, immunosuppressive therapy, cytotoxic therapy and any experimental treatments (see [Table 3](#)).

Table 3: Medications Prohibited for all Participants

Category	Generic Name and Examples of Associated Brand Names
Anti-inflammatory or antipyretic medication: prohibited within 24 hours prior to or after vaccination	Glucocorticoids, aspirin-containing medication, NSAIDs, acetaminophen-containing medication Motrin, Advil [®] , Co-Advil [®] , Bayer [®] , Tylenol [®] Excedrin [®] Topical hydrocortisone Note: NSAIDs should be used (if medically indicated) with caution (outside 24 hours prior to or after vaccination) by participants in Group 1, because in pre-clinical studies and post-marketing the combination of high doses of quinolones with NSAIDs has been shown to provoke convulsions (see ciprofloxacin prescribing information in the Pharmacy Manual).
Aspirin withheld on each day of vaccination, but may be resumed the following day	Low-dose aspirin (≤ 81 mg/day)
Any commercially-available vaccine (except that for anthrax) through two weeks after the last vaccination	Including but not limited to vaccines for influenza, shingles, hepatitis B, pneumococcal, tetanus, yellow fever, pertussis, cholera, adenovirus, diphtheria, rabies virus haemophilus b, hepatitis A, human papillomavirus, measles, mumps, Japanese encephalitis virus, meningococcal vaccine, polio virus, plague, rotavirus, zoster vaccine, smallpox
Immunomodulatory agents through the final follow-up phone call. Note: inhalation use (eg, for seasonal allergies) is permitted.	Any systemic corticosteroids including, but not limited to, generic and brand names of: betamethasone, budesonide, cortisone acetate, dexamethasone, hydrocortisone, methylprednisolone, prednisolone, prednisone, triamcinolone.
Cytotoxic Therapy	Any of the alkylating agents, platinum coordinating complexes, antimetabolites or natural products used in current therapeutic regimens for cancer or rheumatic diseases including but not limited to generic and brand names of: methotrexate, cyclophosphamide, azathioprine, methotrexate, mercaptopurine, bendamustine, streptozocin, cisplatin, chlorambucil and hydroxyurea.

AV7909 Anthrax Vaccine

IND 014451

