8.1.2.14. Group 1A: Day 37 (± 1 d) – Blood Draw for TNA

The Day 37 visit to draw blood for immunogenicity may shift by ± 1 d. If such a shift in visit day occurs, the participant must remain on ciprofloxacin 500 mg po every 12 hours until the morning of that visit. In the event of such a shift, the participant's required number of doses of ciprofloxacin will vary. The Pharmacy Manual will contain a table detailing the dosing options for the final course of ciprofloxacin given a one-day shift from Day 37.

1. Participants will report to the clinic having taken their morning dose of ciprofloxacin at home.

AV7909 Anthrax Vaccine

IND 014451

Protocol EBS.AVA.210, Version 3.0 (28 October 2019)

2. Review participant's ciprofloxacin supply; count the number of remaining doses and compare to the e-diary record to document compliance; record total remaining in source document and eCRF.
3. Review other e-diary entries with participant. Discuss any changes in the use of concomitant medication as well as any vaccination reactions if still ongoing. Remind participants that they should still use sunscreen and avoid excessive sun exposure and strenuous sports until the Day 51 Final Study Visit.
4. Record concomitant medications.
5. Collect blood sample for TNA assessment.

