10.3. Analysis Populations

There will be four analysis populations for this study:

The Intent-to-treat (ITT) Population will include all participants who are randomized. Participant disposition and baseline demographics will be summarized by IP group (Groups 1, 2 and 3) for the ITT population according to the group into which the participant is randomized.

The Safety Population will include all randomized participants who receive at least one dose of either antibiotic or AV7909. All the safety analyses will be conducted with the Safety Population according to the treatment they received.

The PK Population will include all participants in Group 1A and Group 2A who:

- Received two doses of AV7909 according to the protocol (eg, correct dose no temperature excursion, and within the study-specified windows)
- If in Group 1A, received at least 5 of the 7 in-clinic ciprofloxacin doses between Day 4 through the morning of Day 8 and between Day 31 through the morning of Day 35; or if in Group 2A, received at least 7 of the 9 in-clinic doxycycline doses between Day 2 through the morning of Day 8 and between Day 32 through the morning of Day 38
- Have adequate data for PK analysis for the calculation of AUC_{0-12h} and C_{max} at the Day 8 (both Group 1A and 2A) and Day 35 (Group 1A) or Day 38 (Group 2A) visits,
- Have no protocol deviations that would affect ciprofloxacin or doxycycline PK

Exclusion of participants from population will be done on a case-by-case basis at the time of the PK parameter analysis.

The PK Population will be used for all PK analyses. Participants will be included in the treatment group (ciprofloxacin or doxycycline) according to the antibiotic they received.

The Immunogenicity Population will include all randomized participants who meet the following criteria:

- Received two AV7909 vaccinations according to the protocol (eg, correct dose, no temperature excursion, and within the study-specified windows)

AV7909 Anthrax Vaccine

IND 014451

Protocol EBS.AVA.210, Version 3.0 (28 October 2019)

- Had a valid immunogenicity (TNA) result at Day 1 (pre-vaccination) showing no evidence of previous exposure to anthrax or an anthrax vaccine (ie, TNA below the limit of detection)
- Had a valid immunogenicity (TNA) result at Day 37, within the study specified window
- Participants in Group 1 or 2 should have taken at least 50% of the protocol-specified antibiotic doses

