## **3 DATA CONSIDERATIONS**

### **3.1 Protocol Deviations**

A deviation occurs when site personnel or a participant does not adhere to the protocol's stipulated requirements, whether inadvertently or planned. All identified protocol deviations will be documented (entered in the CRO's Clinical Trial Management System or equivalent), classified, and reviewed on an ongoing basis through out the study according to procedures outlined in the Protocol Deviations Management Plan (PDMP). The final protocol deviation data will be reviewed and locked prior to database lock and incorporated into Study Data Tabulation Model (SDTM).

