### **3.2 Analysis Populations**

There will be four analysis populations for this study:

The Intent-to-treat (ITT) Population will include all participants who are randomized. Participant disposition and baseline demographics will be summarized by IP group (Group 1, 2, and 3) and overall for the ITT population according to the group which the participant is randomized to.

The Safety Population will include all randomized participants who receive at least one dose of either antibiotic or AV7909. Participants will be included in the IP group (Group 1, 2, and 3) according to the treatment they received.

The PK Population will include all participants in Group 1A and Group 2A who:

- Received two doses of AV7909 according to the protocol (e.g., correct dose, no temperature excursion, and within the study-specified windows).
- If in Group 1A, received at least 5 of the 7 in-clinic ciprofloxacin doses between Day 4 through the morning of Day 8 and between Day 31 through the morning of Day

35; or if in Group 2A, received at least 7 of the 9 in-clinic doxycycline doses between Day 2 through the morning of Day 8 and between Day 32 through the morning of Day 38.

- Have adequate data for calculation of the PK parameters ( $AUC_{0-12h}$  and  $C_{max}$ ) at the Day 8 (both Group 1A and 2A) and Day 35 (Group 1A) or Day 38 (Group 2A) visits.
- Have no protocol deviations/events that would affect ciprofloxacin or doxycycline steady state PK assessment or immunogenicity results.

Exclusion of participants from population will be done on a case-by-case basis at the time of the PK parameter analysis.

The PK Population will be used for all PK analyses. Participants will be included in the treatment group (Group 1A or Group 2A) according to the antibiotic received.

The Immunogenicity Population will include all randomized participants who:

- Received two doses of AV7909 according to the protocol (e.g., correct dose, no temperature excursion, and within the study-specified windows).
- Had a valid immunogenicity (TNA) result at Day 1 (pre-vaccination) with no evidence of previous exposure to anthrax or an anthrax vaccine (i.e., TNA below the limit of detection of 0.059).
- Had a valid immunogenicity (TNA) result at Day 37, within the study-specified window.
- Participants in Group 1 or Group 2 should have taken at least 50% of the protocol-specified antibiotic doses.

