## 6.5 PK Analyses

All PK analyses will be conducted based on the PK Population. All PK data listings will be presented based on the Safety Population.

PK concentration data will be summarized by study day and nominal time. The trough concentrations will be summarized by study day. The summary statistics for concentration data will include n, arithmetic mean, SD, median, minimum, maximum, and coefficient of variation (CV%).

PK parameters in **Table 3** will be summarized by study day. Summary of  $t_{max}$  will include n, median, minimum, and maximum only. For other PK parameters, n, arithmetic mean, SD, median, minimum, maximum, coefficient of variation (CV%), geometric mean, and geometric CV% will be presented.

The CV% is computed as:

$$CV\% = 100 \times (SD/Mean).$$

The geometric mean is computed as:

$$\text{Geometric mean} = \exp(\text{arithmetic mean of log transformed data}).$$

The geometric CV% is computed as:

$$CV\% \text{ geometric mean} = (\text{sqrt}(\exp(\text{variance for log transformed data}) - 1)) \times 100.$$

Individual as well as arithmetic mean concentration-time profile plots for serum concentration and trough concentrations will be presented in linear and semi-logarithmic scale.

The scatter plots of individual and geometric mean values for  $AUC_{0-12h}$  and  $C_{max}$  for ciprofloxacin and doxycycline will be presented for single dose and steady state profiles. The scatter plots of individual and geometric mean values for the ratio of  $AUC_{0-12h}$  and  $C_{max}$  will be presented for single dose and steady state profiles.

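### SAP 3.2 lets a deviation that bears only on TNA results remove a participant from the PK Population, where protocol 10.3 allows only PK-related deviations to do so

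*SAP*

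**What the plan says.** Both documents define the PK Population by a list of conditions that must all be met: two AV7909 doses given per protocol, a minimum number of in-clinic antibiotic doses, adequate data for AUC0-12h and Cmax on the two steady-state days, and a condition on deviations. They differ on the last.

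- Protocol 10.3: "Have no protocol deviations that would affect ciprofloxacin or doxycycline PK".
- SAP 3.2: "Have no protocol deviations/events that would affect ciprofloxacin or doxycycline steady state PK assessment or immunogenicity results".

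SAP section 1 says that the SAP is based on protocol Version 3.0. Nothing in the SAP explains the added ground. Both documents leave exclusion to case-by-case judgement when the PK parameters are analysed.

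SAP 6.5 states: "All PK analyses will be conducted based on the PK Population". That covers the paired two one-sided tests for the primary endpoint (SAP 6.5.1) and the single-dose analyses (SAP 6.5.2). Under SAP 2.3.2.3 and 4.8, formal TNA non-inferiority testing for an antibiotic follows only if its primary PK endpoint is met.

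TNA has its own analysis set. Among other conditions, a member of the Immunogenicity Population must have met this one: "Had a valid immunogenicity (TNA) result at Day 37, within the study-specified window".

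**The concern.** The population for the primary analysis should be the one the protocol defines, and its exclusions should relate to the data being analysed. As the SAP is written, a participant whose two steady-state profiles are complete and sound can be dropped from the equivalence test because something went wrong with TNA. The protocol would keep that participant.

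Two things are at stake. First, the SAP departs without explanation from the protocol on who enters the primary test. Second, evaluable PK data can be lost on a ground that is not about PK, in a group of about 40 per antibiotic whose primary result also decides whether TNA is formally tested.

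**Working it through.** **1. Which participants the two wordings treat differently.** Vaccine errors of dose, temperature or timing exclude under both documents through the two-dose condition, so they are not at issue. Deviations that affect antibiotic PK also exclude under both. What remains is a deviation or event that affects immunogenicity results and not PK.

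**2. Clean example: the Day 37 draw in Group 1A.** Protocol 8.1.2.14 says "The Day 37 visit to draw blood for immunogenicity may shift by" one day either way, and SAP 3.4 (Table 2) sets the Group 1A window at Days 36 to 38. The last primary PK profile is scheduled for Day 35. A TNA draw that is missed or out of window cannot alter the Day 8 or Day 35 concentrations.

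| | Protocol 10.3 | SAP 3.2 |
|---|---|---|
| PK Population | stays in | can be excluded |
| Immunogenicity Population | excluded (no valid in-window result) | excluded (same reason) |

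The added words are therefore not needed to protect the TNA analysis here.

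**3. Conditional example: an antipyretic after vaccination 1.** Protocol 6.5.1.1 (Table 3) lists "Anti-inflammatory or antipyretic medication: prohibited within 24 hours prior to or after vaccination". Groups 1A and 2A "will receive their first vaccination after the 12-hour PK sample in the evening of Day 8", so the pre-vaccination profile is complete before the medicine is taken. The post-vaccination profile follows 35 − 8 = 27 days later (ciprofloxacin) or 38 − 8 = 30 days later (doxycycline). However, protocol 7.3.1 (Table 4, item 10) makes receipt of prohibited medication a possible reason to discontinue treatment, by judgement of the investigator with the medical monitor's agreement. A participant stopped before vaccination 2 fails the two-dose condition under both documents. The example holds only for someone who is not discontinued and receives both doses.

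**4. Size: reproduce the planned figures first.** Inputs from protocol 10.2 and SAP 2.4: CV 30%, true ratio 0.95, limits 0.80 to 1.25, 5% per one-sided test, 40 planned, up to 30% excluded. The protocol synopsis adds 34 participants for 95% power.

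- SD of the log ratio: σ = √ln(1 + 0.30²) = √ln 1.09 = 0.2936.
- Given the sample SD s, with t the 95th percentile of Student's t on n − 1 degrees of freedom, the probability of passing is Φ[(ln(1.25/0.95) − t·s/√n) / (σ/√n)] − Φ[(ln(0.80/0.95) + t·s/√n) / (σ/√n)], taken as zero when negative. Power is its average over the chi-square distribution of (n − 1)s²/σ².

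| Evaluable n | Power per parameter |
|---|---|
| 40 | 97.68% |
| 34 | 95.51% |
| 28 | 91.45% |
| 27 | 90.49% |
| 26 | 89.44% |
| 25 | 88.26% |

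The smallest n for 90% is 27 and for 95% is 34, as the documents state. The exclusion allowance leaves 40 × 0.70 = 28.

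**5. Cost per lost participant near the planned minimum.** From 28 to 27: 91.45 − 90.49 = 0.96 points. From 27 to 26: 90.49 − 89.44 = 1.05 points. From 26 to 25: 89.44 − 88.26 = 1.18 points. The documents give no expected number of TNA-only deviations, so the total loss cannot be estimated.

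**The case against.** The strongest reply has four parts.

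*Exclusion is discretionary.* Case-by-case review may well keep a participant whose only fault is a late TNA draw. Whether a missed draw counts at all depends on how the Protocol Deviations Management Plan classifies it, and that plan is not among the documents. This stands: the SAP permits the exclusion and does not require it. Discretion does not supply a PK reason, though.

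*The vaccine response may matter to the PK question.* The trial asks whether vaccination alters antibiotic PK, and both documents already require vaccination per protocol. A deviation that blunted the response could be argued to bear on that. This is a fair inference, and it is why the point does not extend to every immunogenicity deviation. The SAP does not offer it as a reason, and it cannot justify exclusion for a missed blood draw.

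*Safeguards exist.* SAP 3.1 says: "The final protocol deviation data will be reviewed and locked prior to database lock". SAP 5.1 has reasons for exclusion from the PK Population summarised and listed. Both make such exclusions visible. Neither removes the non-PK ground.

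*The allowance absorbs it.* With up to 30% excluded, 28 participants remain and power per parameter is still above 90%. This stands, and it limits the size of the point.

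A reader might also infer that the wording inflates the type I error of the primary test. The documents do not support that. Exclusions that do not depend on the PK results cost power and leave the error rate where it was. Inflation would need someone to choose exclusions by looking at the results, which nothing in the plan suggests, and the same risk would attach to case-by-case PK exclusions under the protocol's own wording.

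**Conclusion.** The discrepancy is real and the SAP wording should change. A participant with complete steady-state profiles can be left out of the primary equivalence test for a deviation that concerns TNA only, which protocol 10.3 does not allow. The clean case is the Group 1A Day 37 draw. The antipyretic case counts only if the participant stays on treatment and receives both vaccine doses.

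The consequence is small. The planned 27 evaluable and 40 enrolled per PK group are unaffected, and power falls by about one point per participant lost near 27. These figures rest on the plan's own CV of 30% and true ratio of 0.95, and they are per parameter. Both AUC0-12h and Cmax must pass, so joint power is no higher than this.

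It would go too far to say that such participants will be excluded, that the study becomes underpowered, or that the false-positive rate rises. The first overlooks the case-by-case rule, the second the 30% allowance and the lack of any stated deviation rate, and the third requires results-driven selection.

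**What to change.** In the PK Population criterion of SAP 3.2, delete the words *or immunogenicity results*, so that the deviation ground is PK only, as in protocol 10.3. If the sponsor intended the wider ground, the SAP should give the reason and the two documents should be aligned before database lock.

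Deletion alone does not make the texts identical. Two differences need reconciling in the same edit:

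- The SAP speaks of *deviations/events*, the protocol of deviations.
- The SAP refers to *steady state PK assessment*, the protocol to PK generally. This matters because the same population also serves the single-dose analyses in SAP 6.5.2.

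The cost is one phrase deleted and two terms aligned in SAP 3.2, with no change to data collection, sample size or planned tables.

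A separate, optional suggestion is to settle deviation-based exclusions after the deviation data are locked and before the PK parameters are reviewed. That would alter the timing sentence common to both documents, so both would have to be amended. Exclusions for inadequate AUC0-12h or Cmax data would stay at the PK analysis, because under SAP 6.4 they can depend on whether the elimination rate constant is estimable.

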## 5 STUDY POPULATION CHARACTERISTICS

### 5.1 Subject Disposition

Subject disposition will be displayed in form of tabulation and listing for all participants who signed and dated the ICF. Tabulations will include the number of participants screened, randomized, treated with any study treatment, completed the study, discontinued study treatment, and study withdrawal. Reasons for discontinuation of treatment and study withdrawal will be summarized.

The participant last study visit will be summarized by treatment group and overall for all randomized participants. The number and percentage of participants randomized by site will be provided by treatment group and overall based on the ITT population. Reasons for screen failure and reasons for exclusion from PK Population and Immunogenicity Population will be summarized.

Listings of participants excluded from the PK Population and Immunogenicity Population with reasons will be provided.

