### **6.2 Exclusion of Outliers**

Individual serum concentrations may be excluded from the analysis because they are erroneous or abnormal at the discretion of the pharmacokineticist following a review of available documentation (e.g., bioanalytical report, validation report) and communication with the sponsor. Any such exclusion will be clearly listed in the study report along with justification for exclusion.

Entire serum concentration-time profiles for a participant may be excluded following review of available documentation (e.g., bioanalytical report, validation report, and protocol deviation log) and communication with the sponsor. However, results of analysis with and without the excluded profiles may be presented in the study report. Any such exclusion will be clearly listed in the study report along with justification for exclusion.

Any excluded data will be flagged in the individual data listings.

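### Part of the PK exclusion is left to judgement at the PK analysis stage and no unexcluded result is required, so the primary equivalence verdict can depend on exclusions made with the concentrations in view

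*SAP*

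**What the plan says.** SAP section 3.2 gives four conditions for the PK Population: both vaccinations per protocol; at least 5 of 7 (Group 1A) or 7 of 9 (Group 2A) in-clinic antibiotic doses before the steady-state sessions; adequate data to calculate AUC0-12h and Cmax at both steady-state sessions; and no deviation or event that would affect the PK or immunogenicity results. It then says: "Exclusion of participants from population will be done on a case-by-case basis at the time of the PK parameter analysis". Protocol section 10.3 has the same sentence. Its deviation condition is narrower, because it mentions neither events nor immunogenicity.

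SAP section 6.2 adds two further routes:

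- Concentrations: "Individual serum concentrations may be excluded from the analysis because they are erroneous or abnormal at the discretion of the pharmacokineticist", after review of documentation and communication with the sponsor.
- Profiles: "Entire serum concentration-time profiles for a participant may be excluded following review of available documentation", again with communication with the sponsor.

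For profiles only, "results of analysis with and without the excluded profiles may be presented in the study report". The safeguards in section 6.2 are: "Any such exclusion will be clearly listed in the study report along with justification for exclusion" and "Any excluded data will be flagged in the individual data listings". Section 5.1 adds: "Reasons for screen failure and reasons for exclusion from PK Population and Immunogenicity Population will be summarized".

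**The concern.** The primary claim for each antibiotic is equivalence: the 90% CIs for AUC0-12h and Cmax must both lie within 0.80 to 1.25 (SAP 2.3.1 and 6.5.1). In such a test, removing extreme post/pre ratios narrows the interval, and removing ratios on one side also shifts the estimate. Both changes favour a conclusion of no effect.

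SAP section 4.8 states 5% type I error per parameter. That holds only if exclusions do not depend on the result. The same primary result also decides whether immunogenicity is formally tested for that antibiotic. The trial is open-label and each participant is his or her own control, so nothing in the design hides which session a concentration came from. If exclusions are judged with concentrations available and no unexcluded interval is required, a reader of the report cannot tell whether the verdict depends on them.

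**Working it through.** **Where judgement enters**

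| Step | Rule in the SAP | Result without the exclusion |
|---|---|---|
| Vaccination and dose counts (3.2) | Objective | None planned |
| Adequate data (3.2, 6.1, 6.4) | Partly rule-based; partial data judged case by case | None planned |
| Deviations or events that would affect PK (3.2) | Judgement; no list | None planned |
| Single concentrations (6.2) | Erroneous or abnormal; no numeric criterion | None planned |
| Whole profiles (6.2) | Document review; no criterion | Optional |

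Section 6.4 does give a numeric rule for an anomalous pre-dose value (above 5% of Cmax), but only for single-dose days. The steady-state sessions, which carry the primary test, have no counterpart.

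**The plan's own figures**

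Inputs (SAP 2.4, protocol synopsis): CV of the ratio 30%, true ratio 0.95, bounds 0.80 and 1.25, 5% per side, 40 enrolled per PK group, up to 30% excluded.

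- SD of the log ratio = √ln(1 + 0.30²) = 0.2936.
- Exact paired TOST power: n = 27 gives 90.5% (n = 26 gives 89.4%); n = 34 gives 95.5%; n = 40 gives 97.7%. The stated 27 for 90% and 34 for 95% reproduce.
- 27 / (1 − 0.30) = 38.6, so 39 are needed and 40 is enough. 30% of 40 is 12 exclusions, leaving 28.

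**Why a few exclusions matter**

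With n = 40, the half-width of the log-scale 90% CI is about 1.685 × 0.2936 / √40 = 0.078. The observed ratio must therefore exceed about exp(ln 0.80 + 0.078) = 0.865 to clear the lower bound. In simulation, each of the first four removals of the lowest remaining ratio raises the geometric mean ratio by about 1.2 to 1.6%.

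**Type I error at a true ratio of exactly 0.80**

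Simulated paired TOST, one parameter, log SD 0.2936, at least 100,000 trials per setting. Ranges run from n = 40 to n = 28 before removal.

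| Ratios removed | Unrelated to the result | Farthest from the median, either side | Lowest (worst case) |
|---|---|---|---|
| 0 | 5% | 5% | 5% |
| 1 | 5% | 7-8% | 11-12% |
| 2 | 5% | 9-11% | 19-21% |
| 3 | 5% | 11-13% | 28-32% |

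**Both parameters required**

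Suppose AUC0-12h and Cmax both have a true ratio of 0.80, with an assumed correlation of 0.5 to 0.8 and n = 40. The joint false-equivalence rate is then 1.2-2.4% with none removed, 5.9-10.6% with the two lowest removed and 14.9-24.7% with the four lowest removed. If one parameter is clearly equivalent, the single-parameter table is the better guide.

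**The case against.** The best defence is that the discretion is bounded and visible.

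- **Bounded.** A reader might infer from the case-by-case sentence that participants can be dropped freely. The four conditions do not support that. The sentence follows them and can be read as saying how they are applied; it names no separate ground for exclusion and does not mention outlying ratios.
- **Justified.** A reader might infer that exclusion without a reason is allowed. Section 6.2 does not support that either: it requires document review, sponsor communication and a listed justification. What remains is that being abnormal can itself serve as the justification.
- **Timing.** It is tempting to say that exclusions are made with the post/pre ratios known. Section 3.2 does not say this, and section 6.2 gives no timing. Review of a bioanalytical report does imply that concentrations are available. Deviation data are locked before database lock (SAP 3.1), but that fixes the records, not the decision on who is excluded because of them.
- **Visible.** PK listings use the Safety Population (SAP 6.5), so excluded values can be seen. That helps a determined reader, but it does not supply the interval.
- **Partly unavoidable.** Whether AUC0-12h can be calculated may depend on estimating Kel (SAP 6.4). The whole population therefore cannot be fixed from dosing, timing and deviation records before derivation. This point stands, and the fix allows for it.

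**Conclusion.** The point holds as a limited one. Part of the PK exclusion is discretionary at the PK analysis stage, and the plan requires no primary result without the exclusions. The disclosure rules are sound but cannot show whether the verdict depends on them.

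The size depends on how exclusion behaves: no inflation if it is unrelated to the result, about 7-13% for direction-neutral removal of one to three extreme ratios, and about 11-32% if the lowest one to three are removed. These figures assume a true ratio of exactly 0.80, log-normal ratios and a 30% CV, and they cover one parameter. They model removal of participants, not of single concentrations.

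A reader might take the upper figures as a forecast, or as a sign that the sponsor intends selective exclusion. The documents support neither: those figures are a worst case. The sample size is not in question.

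**What to change.** 1. In SAP 6.2, make the with-and-without presentation mandatory and extend it to excluded participants and single concentrations. Report the primary 90% CIs for all Group 1A and 2A participants with calculable AUC0-12h and Cmax at both steady-state sessions, with no discretionary exclusions, beside the PK Population result.
2. Delete the words that allow exclusion for being abnormal. Exclude a concentration or profile only for a documented bioanalytical, collection or dosing error.
3. Decide the vaccination, dose-count and deviation conditions before database lock, from records alone. Leave only the calculability of AUC0-12h and Cmax, under the SAP 6.4 rules, to the PK analysis, and judge it per profile before post/pre ratios are computed.

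The cost is SAP wording and one extra table; the sample size does not change. The downside is that an outlier with no known cause stays in the analysis and may widen the interval.
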